7.3. STEP 3. INTERVENTIONS**7.3a. Subjects:**

Relatives of individuals with Type 1 DM; ages 4-45 years, if staged as High Risk at Step #2, or ages 3-45 years, if staged as Intermediate Risk at Step #2.

7.3b. Procedures:

If a subject meets High Risk or Intermediate Risk criteria at Step #2, the DMU coordinator will review eligibility with Center personnel. Once a patient is deemed eligible, they will be contacted by Clinical Center Trial Coordinator or Physician and an interview scheduled, at which time the trial will be described in detail and informed consent for randomization requested. The appropriate intervention informed consent (*Informed Consent Form C or D - Intervention Protocols*) will be presented and explained in person, signed, and witnessed. Where appropriate, assent from children should be obtained (age 7-18). This informed consent will explain full details of randomized intervention trial. Individuals who agree to participate will be randomized by DMU. A maximum of 4 weeks may elapse between randomization and initiation of any treatment protocol.

7.3c. Eligibility Criteria for Randomization (Generic for Both Parenteral Antigen and Oral Antigen Protocols):**A. Inclusion:**

1. Willing to volunteer for randomization, give informed consent to participate in intervention protocol for which subject is eligible, and commit to adherence to treatment group assignment.
2. Age: 4-45 for parenteral antigen protocol; 3-45 for oral antigen protocol.
3. Relative of patient with Type 1 DM: primarily first degree relatives but second and third degree relatives (nieces, nephews, aunts, uncles, grandchildren, cousins) age 20 or less allowed. Definition of "Type 1 DM" in proband: proband's diabetes onset prior to age 40 and receiving insulin therapy within one year of diagnosis. (This definition is used to limit inadvertent screening of relatives of probands with Type 2 DM, and is not intended to exclude relatives of persons who have Type 1 DM but in whom onset was after age 40. If there is ambiguity as to eligibility, such as whether a proband has Type 1 DM, this will be resolved by an Eligibility and Events Committee.)
4. ICA Positive: ≥ 10 JDF units confirmed on two tests.

B. Exclusion:

1. History of treatment with insulin or oral hypoglycemic agent.

2. Diabetes by 1997 ADA criteria:
 - fasting plasma glucose \geq 126 mg/dL, or
 - 2 hour plasma glucose \geq 200 mg/dL.(An OGTT must be performed within 3 weeks of randomization into an intervention protocol).
3. HLA-DQA1*0102,DQB1*0602
4. Known severe active disease, e.g. chronic active hepatitis, severe cardiac, renal, hepatic, immunodeficiency and/or disease which is likely to limit life expectancy or lead to therapies such as immunosuppression during the time of the study.
5. Prior participation in trial for prevention of Type 1 DM, e.g. nicotinamide, insulin, immunosuppressive drugs. However, individuals known to be in placebo arm of a completed prior prevention trial, if meeting all other criteria, will be eligible for DPT-1 trial.
6. History of therapy with immunosuppressive drugs or glucocorticoids within past two years for a period of more than 3 months.
7. Ongoing use of medications known to influence glucose tolerance, i.e. sulfonylureas, metformin, diphenylhydantoin, thiazide or other potassium depleting diuretics, beta-adrenergic blockers, niacin. Patients on such medications should be changed to a suitable alternative and will become eligible one month after discontinuation.
8. Individuals deemed unable or unlikely to comply with protocol.
9. Pregnancy or planned pregnancy within the time frame of the study. Women of child bearing potential are not excluded from participation. Individuals will be advised not to volunteer for the study if they plan to become pregnant during the time of the study. If pregnancy occurs, protocol will be interrupted for the duration of the pregnancy. Low dose estrogen oral contraception is permitted. For the High Risk Protocol, a negative pregnancy test must be obtained in women of child bearing potential prior to each admission for periodic intravenous insulin infusion.

7.3d. Eligibility Criteria (Parenteral Antigen Protocol):

A. Inclusion:

1. Categorized as High Risk in Step #2, on basis of age, type of relative, IVGTT, IAA, and OGTT.
2. OGTT that is non-diabetic by 1997 ADA criteria.

B. Exclusion:

1. Unwilling or unable or unlikely to come for periodic intravenous infusions.
2. Unwilling or unable or unlikely to perform daily insulin injections.
3. Unwilling or unable or unlikely to comply with follow-up evaluations.

7.3e. Eligibility Criteria (Oral Antigen Protocol):**A. Inclusion:**

1. Categorized as Intermediate Risk in Step 2, on basis of age, type of relative, IVGTT, IAA.
2. Normal glucose tolerance by 1997 ADA criteria:
 - fasting plasma glucose < 110 mg/dL and
 - 2 hour plasma glucose < 140 mg/dL and

B. Exclusion:

1. Unwilling or unable or unlikely to comply with follow-up evaluations.
2. OGTT that reveals Diabetes (see Generic Eligibility Criteria above), Impaired Glucose Tolerance (IGT), or Impaired Fasting Glucose (IFG) by 1997 ADA criteria.

IGT is defined by:

- fasting plasma glucose < 126 mg/dL, and
- 2 hour plasma glucose 140-199 mg/dL, and

IFG is defined by:

- fasting plasma glucose 110-125 mg/dL AND
- 2 hour plasma glucose < 140 mg/dL

(Subjects with IGT or IFG are eligible for the High Risk Parenteral Trial).

7.4. COMPLETION OF ENROLLMENT IN PARENTERAL STUDY, UPDATING OF STUDY INFORMATION ON THESE SUBJECTS, & ACTIONS FOR INDIVIDUALS SUBSEQUENTLY IDENTIFIED AS "HIGH RISK"**7.4a. Completion of Enrollment:**

The *High Risk Parenteral Trial* completed enrollment on October 31, 2000, with 339 subjects having been randomized.

7.4b. Updating of Study Information on Subjects in High Risk Parenteral Trial:

On the recommendation of the Data Safety and Quality Monitoring Group (DSQ), the Steering Committee initiated a “Study Update” for the High Risk Parenteral Trial on November 1, 2000. The DPT-1 Task Force on Contingency Planning earlier had developed a procedure for a detailed “Study Update”, the purpose of which is to obtain complete follow-up information on all subjects randomized in either trial – in this case, the High Risk Parenteral Trial. The “Study Update” is designed to allow determination of diabetes status on all subjects, including resolution of all ambiguities, since some subjects may have had one abnormal OGTT without confirmation. It also provides a complete data set for all DPT-1 study parameters, so that it will be possible to perform data analysis to determine all outcomes, on the assumption that this “Study Update” may equate with “End of Study” data collection.

Commencing November 1, 2000, all subjects who have ever been randomized in the Parenteral Study (unless already diagnosed as having diabetes within DPT-1) will be asked to come in to complete all DPT-1 evaluations not recently performed. The Study Update period will span 5 months, through March 31, 2001. The mid-point of that period is January 15, 2001. That date will be used for data analysis and to define windows for completion of tests.

The DPT-1 evaluations need to be performed include: oral glucose tolerance (OGTT) test and HbA1c if not performed in the 3 month window prior to January 15, 2001; mixed meal tolerance test (MMTT), intravenous glucose tolerance test (IVGTT), wide range achievement test (WRAT), and islet cell auto-antibodies (ICA and insulin) if not performed in the 6 month window prior to January 15, 2001. Of the tolerance tests – each of which must be performed on a separate day – the first priority is the OGTT, next the MMTT, and last the IVGTT. Some subjects may need second or third OGTTs as well, to confirm or refute suspected but unconfirmed diabetes.

Subjects will need to be scheduled in the most convenient way possible, with the plan to complete all testing by March 31, 2001. Every effort will be made to contact every subject randomized – regardless of whether or not they have been seen recently, and whether or not they are still participating in DPT-1.

During the Study Update, all randomized subjects will continue their assigned treatment. For those in the experimental group, both subcutaneous injections and insulin infusions should continue. For those in the closely monitored group, no insulin will be taken.

7.4c. Subjects Identified as “High Risk” after Close of Enrollment in the Parenteral Trial:

Subjects who are identified as “High Risk” after the close of enrollment in the Parenteral Study, will be followed closely for the development of diabetes, as they would be if they had been randomized. It will be explained to them that enrollment has been completed, that data are being collected to determine the results of the High Risk Parenteral Trial, and that a recommendation will be made to them as soon as the information is available. They will have the opportunity to participate in the debriefing to be offered to all subjects randomized in the High Risk Parenteral Trial.

8. INTERVENTION PROTOCOL - HIGH RISK COHORT (Parenteral Antigen)**8.1. Summary:****Randomized to One of Two Treatment Arms - Experimental Group and Closely Monitored (Control) Group**

The *Experimental Group* will receive:

- Continuous intravenous insulin infusions consisting of:
 - Recombinant human regular insulin
 - Every 12 months (acceptable window \pm 6 weeks) for
 - 4 consecutive days duration
 - Blood glucose will be monitored q 1 h during daytime, q 2 h at night, and
 - Adjusted by algorithm
- Chronic subcutaneous insulin
 - Recombinant human long-acting ultralente insulin at an
 - Initial dose 0.25 units/kg/day
 - Dose of insulin will be divided 50% before breakfast in morning, 50% at bedtime
 - Dose altered by algorithm
 - Capillary blood glucose profile measurements every 3 months (consisting of 5 samples - before breakfast, before lunch, before supper, two hours after supper, and 3:00AM)
- Intervening outpatient visit, will occur
 - Halfway between admissions for IV infusions, i.e. every 6 months
- Oral glucose tolerance testing every 6 months

The *Closely Monitored (Control) Group* will receive:

- Outpatient visits every 6 months
- Capillary blood glucose profile measurements every 3 months (consisting of 5 samples - before breakfast, before lunch, before supper, two hours after supper, and 3:00AM)
- Oral glucose tolerance testing every 6 months

8.2. Baseline Evaluation

By baseline, all subjects will have a Mixed Meal (Boost® [previously known as Sustacal]) Tolerance Test (MMTT) for evaluation of pancreatic β -cell function by measurement of plasma C-peptide responses to this provocative mixed meal challenge. Baseline glycosylated hemoglobin (HbA1c) will be measured in the Core Laboratory. The Wide Range Achievement Test (WRAT) will be performed.

8.3. Protocol for Periodic Admissions for Intravenous Infusion:

Periodic intravenous infusions will be conducted during inpatient admissions to a General Clinical Research Center (GCRC) or equivalent facility. The target for intravenous insulin treatment is intravenous insulin, continuously, for four consecutive days, every 12 months. The definitions in regards each of these components are as follows:

- intravenous insulin - no other route of insulin administration is acceptable. (The intravenous infusion may be performed either with a bedside pump or a portable minipump).
- continuously - three interruptions in the insulin infusion up to a maximum of four hours each will be allowed
- four consecutive days - a minimum duration of two consecutive days is required to be considered as a completed infusion
- acceptable window for infusion is 12 months \pm 6 weeks (the scheduling is based on the date of the original infusion, and every 12 months thereafter)

Insulin infusions not fulfilling any of the above criteria will not be considered as having been administered.

Insulin infusions that are not “acceptable” by the above protocol definition should not be routinely repeated. However, if an infusion is electively terminated prematurely for an unusual event, the subject may be rescheduled for said infusion, as convenient.

Prior to admission, subcutaneous insulin injections must be omitted for 72 hours. *In women of child bearing potential, a negative pregnancy test must be obtained prior to each admission for periodic intravenous infusion.*

DIABETES PREVENTION TRIAL - TYPE 1 DIABETES (DPT-1)

PROTOCOL

Page 36

July 2000 Version

The following are two sample schedules:

Schedule A (Tolerance Testing performed during admission):

Day 1. (Afternoon or Evening). Admission to the GCRC or equivalent facility.

Admission testing and physical examination.

Diet: isocaloric, served as 3 meals with no concentrated sweets, at 0800, 1200, and 1700, and consumed over a 40 minute time period. An evening snack (at 2000) containing 10% of the daily calorie allocation, will be provided to all subjects. Otherwise, only non-caloric snacks are permitted.

Overnight fast (10-16 hours).

Day 2. Determine fasting plasma glucose in local laboratory.

Glycosylated hemoglobin (HbA1c) in Core Laboratory.

OGTT.

Day 3. Determine fasting plasma glucose in local laboratory.

~0800 - Tolerance test -

Mixed Meal (Boost® [previously known as Sustacal]) Tolerance Test (MMTT) or IVGTT.

~1200 - Commence first day of intravenous infusion (following test).

Day 4. 1200 - Commence second day of intravenous infusion

Day 5. 1200 - Commence third day of intravenous infusion

Day 6. 1200 - Commence fourth day of intravenous infusion

Day 7. 1200 - Complete intravenous infusion

Take subcutaneous injection

Discharge subject.

Schedule B (OGTT performed separately):

Day 1. (Morning). Admission to the GCRC or equivalent facility, following overnight fast (10-16 hours).

Admission testing and physical examination.

Determine fasting plasma glucose in local laboratory.

Glycosylated hemoglobin (HbA1c) in Core Laboratory.

~0800 - Tolerance test -

Mixed Meal (Boost® [previously known as Sustacal]) Tolerance Test (MMTT) or IVGTT.

~1200 - Commence first day of intravenous infusion (following test).

Diet: isocaloric, served as 3 meals with no concentrated sweets, at 0800, 1200, and 1700, and consumed over a 40 minute time period. An evening snack (at

2000) containing 10% of the daily calorie allocation, will be provided to all subjects. Otherwise, only non-caloric snacks are permitted.

Day 2. 1200 - Commence second day of intravenous infusion

Day 3. 1200 - Commence third day of intravenous infusion

Day 4. 1200 - Commence fourth day of intravenous infusion

Day 5. 1200 - Complete intravenous infusion

Discharge subject.

8.4. Details of Intravenous Infusion:

The infusion will consist of Humulin®-R human regular insulin in 0.45% (half-normal) saline, administered on a schedule such as that outlined here:

Goals

- Maintain whole blood glucose 60-80 mg/dL (plasma glucose 70-92 mg/dL)
- Avoid Hypoglycemia

Infusion

- Insulin Concentration:
 - 10 units per 500 ml for subjects who weigh less than 50 kg
 - 25 units per 500 ml for subjects who weigh 50 kg or more
- Initial Basal Insulin Rate:
 - 0.015 U/kg/hr (0.15 ml/kg/hr)

Dose alterations:

- “Incremental Increase Amount”: 10% of initial basal rate, calculated in ml/hr, and rounded up to nearest whole number (once established, this does not vary for any infusion period)
- “Incremental Decrease Amount”: twice the “Incremental Increase Amount”, calculated in ml/hr (once established, this does not vary for any infusion period)

Dose limitations:

- Maximum Infusion Rate - 0.08 U/kg/hr (rounded to nearest ml/hr)

DIABETES PREVENTION TRIAL - TYPE 1 DIABETES (DPT-1)

PROTOCOL

Page 38

July 2000 Version

- Minimum Infusion Rate - 0.002 U/kg/hr (rounded to nearest ml/hr) [except when interrupted for whole blood glucose < 50 mg/dL (plasma glucose < 57 mg/dL)]

Monitoring:

- Glucose values are checked every 60 minutes during the day (0800 to 2200), and every two hours from 2200 to 0800.
- With meals, additional glucose value measured 90 minutes after meal
- If change is made in infusion rate, recheck glucose level after one hour
- If hypoglycemia documented - [whole blood glucose < 60 mg/dL (plasma glucose < 70 mg/dL)] - reduce infusion rate and re-check glucose value after 10 minutes

Adjustments in Insulin Infusion Rate:

- For meals (food served at T0):
 - twice premeal basal rate (rate at T0) from T0 to T30 (0-30 minutes after start of meal)
 - three times premeal basal rate (rate at T0) from T30 to T60
 - twice premeal basal rate (rate at T0) from T60 until whole blood glucose \leq 80 mg/dL (plasma glucose \leq 90 mg/dL) or T180
 - then resume premeal basal rate (rate at T0)
- For bedtime snack (served at 2000 hours):
 - 2 times presnack basal rate (rate at T0) from 2000 to 2030 (0-30 minutes after start of snack)
 - then resume presnack basal rate (rate at T0)
- For whole blood glucose < 60 mg/dL (plasma glucose < 70 mg/dL) - reduce current basal rate by “incremental decrease amount”
- For whole blood glucose < 50 mg/dL (plasma glucose < 57 mg/dL) or mild symptomatic hypoglycemia - treat with 4 oz orange juice or 15 gm carbohydrate p.o. and stop (interrupt) insulin infusion. Repeat glucose measurement every 10 minutes, retreat if whole blood glucose < 50 mg/dL (plasma glucose < 57 mg/dL), and restart insulin infusion when whole blood glucose \geq 60 mg/dL (plasma glucose \geq 70 mg/dL) at a new basal rate reduced by

“incremental decrease amount” for each whole blood glucose < 50 mg/dL (plasma glucose < 57 mg/dL)

- For whole blood glucose > 80 mg/dL (plasma glucose > 90 mg/dL) at basal rate- “increase amount” (up to maximum dose of 0.08 U/kg/hr)

8.5. Protocol for Subcutaneous Injections:

All subjects randomized to the experimental group will administer twice daily subcutaneous injections of Humulin®-U human ultralente insulin, given every morning before breakfast and every evening at bedtime, at an initial total daily dose of 0.25 units/kg (each injection containing 0.125 units/kg), using U-100 0.3 or 0.5 cc 29 or 30 g insulin syringes.

- The dose will be adjusted at interim visits as the subject’s weight changes, maintaining equal doses in each injection.
- Hypoglycemic events will be recorded. If mild hypoglycemic symptoms occur, the subjects and their families will be instructed to perform capillary blood glucose monitoring for confirmation of hypoglycemia. If the capillary sample shows a value < 50 mg/dL, the dose will be reduced by 10% (to the nearest 0.5 unit, with a minimum decrease of 0.5 unit).
- There will be no planned increases in dose except those associated with weight gain consequent to normal growth.
- During the first week after initiation of subcutaneous insulin, daily fasting glucose will be measured by home capillary blood glucose monitoring.
- At the end of the first week, and thereafter every three months, and one week following any dosage change, subjects will perform 5-point (before meals, 90-120 minutes after dinner, and 3:00AM) glucose profiles by home capillary blood glucose monitoring. If asymptomatic hypoglycemia (capillary blood glucose < 50 mg/dL) is detected on more than one sample, the dosage of each insulin injection will be reduced by 10% (to the nearest 0.5 unit, with a minimum decrease of 0.5 unit).
- Two months following any dosage reduction, 50% of the reduction will be restored (to the nearest 0.5 unit, with a minimum increase of 0.5 unit).

- During intercurrent illness, if hypoglycemia occurs, subcutaneous insulin injections may be omitted for up to 3 days, at the discretion of the Clinical Center physician.

8.6. Follow-up Evaluations:

Subjects in both arms of the study (experimental group and Closely Monitored (Control) Group) will be seen every 6 months. For subjects in the experimental group, these visits must be within 3 weeks of the time of their admission for intravenous infusion, i.e. every 12 months, and at an Intervening Outpatient Clinic Visit halfway between admissions for IV infusions, i.e. every 6 months. In both groups, on each of these occasions:

- Physical examination will be performed. Height and weight will be recorded.
- HbA1c will be determined by the Core Laboratory (as a secondary indicator both of potential diabetes if above the upper limit of normal, and as a secondary indicator of hypoglycemia if below the lower limit of normal)
- OGTT will be performed (primary study outcome). Subcutaneous injections will be omitted for 72 hours prior to OGTT. Subjects will have adequate dietary preparation (minimum 150 g carbohydrate per day) for three days prior to OGTT. OGTT will be postponed if there is intercurrent illness, but should be performed no later than 6 weeks after each 6 month anniversary date
- Blood glucose test strips will be provided to the subject.
- Islet cell autoantibodies (ICA) and insulin autoantibodies (IAA) will be determined by the appropriate Core Laboratory, as scheduled (ICA annually, IAA each 6-month visit)

In the experimental group, the following also will be done:

- Dose of subcutaneous insulin will be adjusted based on body weight
- Vials of insulin and syringes will be provided to the subjects.

In both treatment groups, every 12 months, an additional tolerance test will be performed, as follows:

- A Mixed Meal (BOOST® [previously known as Sustacal]) Tolerance Test (MMTT) at the end of years 1, 3, and 5
- An IVGTT at the end of years 2, 4, and 6

In both treatment groups, every three months, subjects will perform 5-point (before meals 90-120 minutes after dinner, and 3:00AM) glucose profiles by home capillary blood glucose monitoring, with results recorded and sent to the Clinical Center Trial Coordinator. If significant

hyperglycemia (capillary blood glucose > 200 mg/dL) is detected on more than one sample, the Clinical Center Trial Coordinator will be notified, and consideration given for early performance of an OGTT.

8.7. Adverse Events Monitoring:

Adverse events will be carefully sought in all subjects. A toll-free 800 telephone line, based at the Data Management Unit (DMU), will be used by all subjects to report all adverse events. This computer based system, using simulated speech (in English or Spanish), ensures that there is uniform review of all symptoms, and allows rapid centralized tracking of all adverse events. The Clinical Center and Affiliate (if monitoring intervention) are notified immediately of any such adverse event by automated facsimile transmission.

In addition, at each visit, subjects are carefully interviewed with regards any adverse events that may have occurred.

The Wide Range Achievement Test (WRAT) will be performed at baseline, six months after enrollment, and on an annual basis thereafter in subjects ages 5-18 at time of enrollment or who attain age 5 during the study. In addition, information about accidents (including motor vehicle accidents) and school performance, will be sought.

Any Study Group member learning of the death of a subject immediately follow the "Notification of Death Procedure" (included in the Manual of Operations).

9. OUTCOME EVALUATION - HIGH RISK COHORT (Parenteral Antigen)

The principal study outcome is the development of diabetes (by criteria established by the American Diabetes Association in 1997). The Oral Glucose Tolerance Test (OGTT) is the principal study outcome test used to detect diabetes. Oral glucose is administered in a dose of 75 grams (in adults) or 1.75 g/kg body weight to a maximum of 75 grams (in children), as a solution in flavored water, consumed within 5 min. Two baseline samples will be obtained (at -10 and 0 minutes) before glucose is consumed. Blood samples will be obtained at 30, 60, 90, and 120 minutes after glucose consumption is complete, for the determination of glucose and C-peptide levels.

A Study Event (or Treatment Failure) is defined as the development of diabetes, by criteria modified from the “adult” criteria established by the American Diabetes Association in 1997. As used in DPT-1, those criteria, which must be met on two occasions (unless criteria [iv] is present) are:

[i] casual (any time of day without regard to time since last meal) plasma glucose \geq 200 mg/dL, if accompanied by unequivocal symptoms (i.e. polyuria, polydipsia, polyphagia, and/or weight loss),

OR

[ii] fasting (no caloric intake for at least 8 hours) plasma glucose \geq 126 mg/dL (core laboratory),

OR

[iii] 2-hour plasma glucose \geq 200 mg/dL during a 75 gram oral glucose tolerance test (OGTT),

OR

[iv] unequivocal hyperglycemia with acute metabolic decompensation (e.g. ketoacidosis).

N.B. In DPT-1, unless criteria [iv] is present or the fasting glucose is \geq 250 mg/dl (at the bedside or in the local laboratory on the day of testing), it is preferred that at least one of the two testing occasions involve an oral glucose tolerance test (OGTT). If the first criterion met is [iii], i.e. by the 2-hour OGTT value, the OGTT should be repeated within 60 days. It is essential that every effort be made to obtain the necessary tests to establish the diagnosis of diabetes.

For fasting hyperglycemia, a tentative diagnosis may be made, based on measurements made in a local laboratory if FPG \geq 160 mg/dL on two separate days within one week, with confirmation by FPG \geq 126 mg/dL on two separate days within one week, as performed in the Core Laboratory. OGTTs will be scheduled every 6 months. If a single OGTT meets the criteria for diabetes, a repeat OGTT will be scheduled within 2 months. There will be strict attention to detail in the performance of OGTTs. Subcutaneous injections will be omitted for 72 hours prior to OGTT.

Subjects will have adequate dietary preparation (minimum 150 g carbohydrate per day) for three days prior to OGTT. OGTT will be postponed if there is intercurrent illness, but must be performed no later than 6 weeks after each 6 month anniversary date.

If a diagnosis of diabetes is made outside of the study, the Eligibility and Events Committee will review the criteria for establishing the diagnosis. The subject will be asked to complete all measures that are scheduled for collection at the time of a Study Event or Study End.

As a subsidiary outcome, pancreatic β -cell function will be assessed by measuring C-peptide response during each OGTT.

Subjects will have a Mixed Meal (Boost® [previously known as Sustacal]) Tolerance Test (MMTT) at the end of year 1, year 3, year 5, and at the time of their completion of intervention (either if there is a Study Event, i.e. Treatment Failure, or at Study End). For those subjects who develop diabetes, the MMTT at Study End will be performed 8-16 weeks after the diagnosis has been made, having withheld long acting insulin the night before and all insulin the morning of the MMTT. If fasting blood sugar is greater than 250 mg/dl, the MMTT will not be performed, and then only a fasting C-peptide will be measured.

Subjects will have an IVGTT at the end of year 2, year 4, year 6, and at Study End, unless the subject has developed diabetes, in which case the IVGTT will not be performed.

During any MMTT or IVGTT, pancreatic β -cell function will be assessed by measuring C-peptide responses during these provocative challenges.

The sequence for performing tests when more than one are due in any one evaluation period is: OGTT (glucose primary end point) > MMTT (C-peptide secondary end point) > IVGTT. Tests must be performed in the fasting state on separate days.

HbA1c and ICA and IAA will be determined as well. The WRAT should be administered.

10. INTERVENTION PROTOCOL - INTERMEDIATE RISK COHORT (Oral Antigen)**10.1 Summary:****Randomized to One of Two Treatment Arms - Experimental Group and Control Group**

The *Experimental Group* will receive:

- Oral insulin
 - Recombinant human insulin crystals
 - Dose: 7.5 mg/day as single daily dose one-half hour before breakfast
 - Taken as capsule (or, if the subject cannot swallow capsules, dissolved in juice or sprinkled on food)
- Outpatient visits every 6 months
- Oral glucose tolerance testing every 6 months
- Intravenous glucose tolerance testing every 12 months
- Mixed meal tolerance testing every 36 months

The *Control Group* will receive:

- Oral placebo
 - Placebo crystals similar in appearance and taste to oral insulin crystals
 - Dose: volume equivalent to oral insulin (7.5 mg/day) as single daily dose one-half hour before breakfast
 - Taken as capsule (or, if the subject cannot swallow capsules, dissolved in juice or sprinkled on food)
- Outpatient visits every 6 months
- Oral glucose tolerance testing every 6 months
- Intravenous glucose tolerance testing every 12 months
- Mixed meal tolerance testing every 36 months

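### The initial intravenous insulin rate in Protocol Section 8.4 is given as two figures that agree at neither listed concentration; the ml figure delivers one fifth or one half of the stated dose

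*Protocol*

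**What the plan says.** Section 8.4 describes the infusion given to the experimental group of the parenteral trial. It fixes two bag concentrations by weight: "10 units per 500 ml for subjects who weigh less than 50 kg" and "25 units per 500 ml for subjects who weigh 50 kg or more". It then gives a single initial basal rate for everyone, "0.015 U/kg/hr (0.15 ml/kg/hr" (bracket closed after the ml figure).

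The starting rate feeds into later rules of the same section:

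- The increase step is "10% of initial basal rate, calculated in ml/hr, and rounded up to nearest whole number". The decrease step is twice the increase step. Of each it is said that "once established, this does not vary for any infusion period".
- Meal and snack rates are multiples of the basal rate running when food is served: twice for the first 30 minutes of a meal, then three times for the next 30.
- The limits are stated in dose units: "Maximum Infusion Rate - 0.08 U/kg/hr (rounded to nearest ml/hr" and "Minimum Infusion Rate - 0.002 U/kg/hr (rounded to nearest ml/hr" (brackets likewise closed).

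The whole is introduced as "administered on a schedule such as that outlined here". Section 7.4b says that infusions continue for the experimental group during the Study Update.

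**The concern.** The bracket is printed as the volume equivalent of the dose, and a pump is set in volume per hour. With two concentrations, one ml/kg/hr figure cannot equal one U/kg/hr figure for all subjects, so the line must be wrong for at least one weight band. The check below shows that it is wrong for both.

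At stake is the delivered dose. A site that sets the pump from the bracket starts lower than the stated dose, locks in smaller steps up and down for that infusion, and gives proportionally less insulin with any meal taken before the rate has been titrated. The band with the larger discrepancy, below 50 kg, will contain children, since entry to the parenteral trial is from age 4.

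**Working it through.** **Inputs, all from Section 8.4.** Concentrations of 10 U and 25 U per 500 ml; initial rate of 0.015 U/kg/hr with 0.15 ml/kg/hr in brackets; increase step of 10% of the initial ml/hr rate, rounded up; decrease step of twice that; limits of 0.002 and 0.08 U/kg/hr.

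**Concentrations.** 10/500 = 0.02 U/ml (below 50 kg); 25/500 = 0.05 U/ml (50 kg or more).

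**Attempt to reproduce the bracket**, using ml/kg/hr = (U/kg/hr) / (U/ml):

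- below 50 kg: 0.015/0.02 = 0.75 ml/kg/hr
- 50 kg or more: 0.015/0.05 = 0.30 ml/kg/hr

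Neither is 0.15. The two printed figures agree only at 0.015/0.15 = 0.10 U/ml, that is 50 U per 500 ml, which the protocol does not list.

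**Dose delivered if the bracket is followed:**

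- below 50 kg: 0.15 × 0.02 = 0.003 U/kg/hr; 0.003/0.015 = 20%
- 50 kg or more: 0.15 × 0.05 = 0.0075 U/kg/hr; 0.0075/0.015 = 50%

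Both lie between 0.002 and 0.08 U/kg/hr, so the limits would not flag the error.

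**Could one digit be misread?** No single value works. If the bracket read 0.75, subjects of 50 kg or more would get 0.75 × 0.05 = 0.0375 U/kg/hr, 2.5 times the stated dose. If it read 0.30, those below 50 kg would get 0.30 × 0.02 = 0.006 U/kg/hr, 40% of it.

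**Effect on the starting rate and steps at two example weights:**

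| | 40 kg, dose figure | 40 kg, bracket | 70 kg, dose figure | 70 kg, bracket |
|---|---|---|---|---|
| Start (ml/hr) | 0.015×40/0.02 = 30 | 0.15×40 = 6 | 0.015×70/0.05 = 21 | 0.15×70 = 10.5 |
| Increase (ml/hr) | 3.0 → 3 | 0.6 → 1 | 2.1 → 3 | 1.05 → 2 |
| Decrease (ml/hr) | 6 | 2 | 6 | 4 |

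**Catch-up.** At 40 kg, going from 6 to 30 ml/hr in steps of 1 takes 24 increases. At one per hour, with glucose above target throughout, that is about a day of a four-day infusion. At 70 kg, (21 − 10.5)/2 = 5.25, so 6 increases.

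**Response to low glucose.** For a 40 kg subject running at 30 ml/hr, a decrease of 2 ml/hr is a cut of 2/30 = 7%; a decrease of 6 ml/hr is 6/30 = 20%.

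**Meal at the untitrated rate.** First-hour insulin = (0.5 × 2 + 0.5 × 3) × basal = 2.5 × basal.

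- 40 kg: 2.5 × 0.60 = 1.5 U by the dose figure; 2.5 × 0.12 = 0.3 U by the bracket
- 70 kg: 2.5 × 1.05 = 2.6 U; 2.5 × 0.525 = 1.3 U

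Such a meal is plausible: the sample schedules in Section 8.3 start the infusion at about 1200 and serve a meal at 1200. It is not typical of the four days, because the meal rate follows the current basal rate, which is titrated.

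**The case against.** The arithmetic is not in dispute; the case on the other side is about weight.

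- **The dose figure probably governs.** It comes first in the line, and the limits are given in U/kg/hr only, to be rounded to ml/hr. Staff must therefore convert from the bag concentration anyway and would be likely to notice the mismatch. This lowers the risk, but nowhere does the protocol say which figure prevails.
- **There are safeguards.** The schedule is introduced as an example, infusions take place in a clinical research center or equivalent, and affiliated centers need certification to give them (Section 15.3b-7). Glucose is checked hourly by day and every two hours at night. Below 50 mg/dL whole blood glucose, or with mild symptoms, the infusion is stopped and carbohydrate given, whichever figure was used at the start. All of this stands and limits the harm. The smaller decrease step between 50 and 60 mg/dL is the one respect in which the bracket is not on the cautious side.
- **No trial result depends on it.** No endpoint or analysis rule uses the starting rate, and Section 8.3 counts an infusion as given by route, continuity, duration and window. This stands.
- **Little time is left.** Enrollment closed on October 31, 2000, the Study Update ends on March 31, 2001, and infusions are annual. A correction now reaches only the late infusions, but Section 7.4b keeps them going, so it is not moot.
- **A review of past infusion records could be large** for something that changes no analysis. This is fair, and such a review should be optional.

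**Conclusion.** The line is wrong as written. The dose and its bracketed volume agree at neither listed concentration, and no single volume figure could agree at both, so neither rounding nor a misread digit explains it. Following the bracket means starting at 20% of the stated dose below 50 kg and 50% from 50 kg, with titration steps reduced to between one third and two thirds of their intended size at the example weights (1 against 3 and 2 against 6 ml/hr at 40 kg; 2 against 3 and 4 against 6 ml/hr at 70 kg).

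The percentages rest only on the printed concentrations and on 0.015 U/kg/hr being the intended dose. The ml/hr examples also depend on the weights chosen, and the catch-up time assumes one increase per hour. Whether any site used the bracket, and whether the Manual of Operations repeats it, cannot be told from the protocol; no actual misdosing is claimed. The point bears on correct dosing and safety, not on the trial's inference, and should be fixed because the error is certain and the repair is small.

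**What to change.** If 0.015 U/kg/hr is the intended dose, replace the bracket with 0.75 ml/kg/hr for subjects below 50 kg and 0.30 ml/kg/hr for subjects of 50 kg or more. If it is not, correct the concentrations or the dose so that all three agree; the choice belongs to the sponsor's clinicians and pharmacy. State that the increase and decrease steps are computed from the corrected ml/hr rate. Check the Manual of Operations for the same line and notify the sites giving the remaining infusions.

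The cost is a one-line protocol correction, one look at the Manual and one site notice. Optionally, note from infusion records already held which starting rate was used, on a sample if a full review is too much work; the correction does not depend on it.
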